### **At 3rd trimester**

Data will be collected about anxiety related to the pregnancy/delivery itself (PES-brief), perceived stress, fetal outcome (SGA in utero from medical records), social support, quality of marital relationships, functional disability and cost of service utilization and behavioral activation. An intimate partner violence (IPV) screening question will be administered so that referrals can be made if any women experience IPV. Women in the biological substudy will also have a blood draw (using same techniques described above under 'baseline visit').

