#### Follow-up (6 weeks postpartum):

The primary endpoint will be assessed at six weeks postpartum (with flexibility for -1 week and +4 week window if needed because of scheduling reasons). Women returning for their routine 6-week postpartum visit will be asked to undergo a final follow-up assessment conducted by the Assessment Team, who will be masked to the allocation status of trial participants. Women in the biological substudy will also have a blood draw (using same techniques described above under 'baseline visit'). We will also administer the *Ages & Stages Questionnaire, Third Edition (ASQ-3)* to the infants of all participants in the trial to assess infant neurobehavioral functioning.

For the detailed description of the outcomes and time points, see **Table 4** below.

In the chart below, data collection procedures that are specific to the substudy are marked as Os in the chart instead of as Xs.

Table 4: Schedule of study assessment activities

	Screening	Baseline *	2 nd trimester	3 rd trimester**	Birth	6 weeks postpartum **
	Time 1	Time 2	Time 3	Time 4	Time 5	Time 6
Informed Consent	X	X				
Eligibility assessment						
Screening step 1 (age, residence, stage of pregnancy, language)	X					
Screening Step 2 (medical exclusions)	X					
Screening Step 3 (HADS anxiety inclusion)	X					
Screening Step 4 (SCID MDE exclusion)	X					
Assessments						
Socio-demographic questions		X				
PSS-10 (stress)				X		X
PES-Brief (pregnancy anxiety)		X		X		
PHQ-9 (depressive symptoms)						X
HADS (anxiety symptoms)	X	O	O			X
HADS (symptoms of depression)	X	O	O			X
MDE diagnosis (from SCID)	X					X
MSPSS (social support)	X		X			X
MRQ (relationships)	X		X			X
Empowerment	X					X
WHO-DAS (disability)	X		X			X
DHS IPV items (violence)						X
IPV Screening Question		X		X		(in the DHS module)
PAAS (behavioral activation)		X		X		X
Breastfeeding					X	X
Parenting self-efficacy						X
PBQ (bonding)						X
MIRI (maternal responsiveness)						X
MSEQ (maternal self-efficacy)						X
Anthropometry§§						X
Economic Data						
CSRI				X		X
Blood Draw (for biology aims)	O	O	O			O
Ages & Stages Questionnaire, Third Edition (ASQ-3)						O
From medical records						
Fetal outcome: SGA in utero*				X		
Pregnancy conditions:				X		
Birth outcomes: SGA, PTB, LBW					X	
Medications	X			X		X

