#### Analysis of Secondary Efficacy Endpoint(s)

We will secondarily compare the intervention and control groups in terms of changes in CMD symptom scores, by measuring depressive symptoms with the 9-item Patient Health questionnaire (PHQ-9) and the HADS anxiety questionnaires. Other outcomes of interest, but not primary targets, include birth outcomes (SGA, LBW, and preterm birth), perceived stress (using the Perceived Stress Scale –PSS), pregnancy-related anxiety (using the Pregnancy Experience Scale PES-Brief), maternal functioning (using WHO-DAS), marital relationships (MacArthur Relationship Questionnaire), IPV, women's empowerment, maternal bonding, maternal responsiveness, child growth at 6 weeks postpartum, as well as initiation and exclusivity of breastfeeding (WHO measures). Pregnancy-related symptoms of anxiety (measured with the PES-Brief) will be assessed at baseline and in the 3rd trimester.

For secondary hypotheses, we will estimate the effects of the intervention using birth and follow-up (6 weeks postpartum) measures separately. Primary analyses will be non-parametric tests, however sensitivity analyses will use parametric models such as linear and logistic regression to control for baseline values of the mothers' characteristics (132). Variable transformations (such as square root or log) will be utilized as appropriate to meet the model assumptions. For primary and secondary endpoints, in all regression models the coefficient on the HMHB vs. non-HMHB (control group) indicator variable will be taken as the estimated effect.

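### PES-Brief pregnancy anxiety is a listed outcome measured only at baseline and in the third trimester, but the rule for estimating secondary effects names only birth and six weeks, so it has no stated between-arm comparison

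*Combined protocol and SAP*

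**What the plan says.** Three places matter, all in Section V of the combined protocol and SAP.

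- **Analysis of Secondary Efficacy Endpoint(s), first paragraph.** The list of other outcomes of interest includes "pregnancy-related anxiety (using the Pregnancy Experience Scale PES-Brief", and the paragraph closes with its schedule: "Pregnancy-related symptoms of anxiety (measured with the PES-Brief) will be assessed at baseline and in the 3rd trimester".
- **Same section, second paragraph.** For secondary hypotheses, "we will estimate the effects of the intervention using birth and follow-up (6 weeks postpartum) measures separately". The main tests are non-parametric. Regression that controls for baseline characteristics is offered as a sensitivity analysis.
- **At 3rd trimester, and Table 4.** The third-trimester visit collects "anxiety related to the pregnancy/delivery itself (PES-brief), perceived stress", fetal outcome from records, and "social support, quality of marital relationships, functional disability and cost of service utilization and behavioral activation". In Table 4 the PES-Brief row is marked at baseline and third trimester, with nothing at birth or six weeks postpartum.

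**The concern.** The two paragraphs of the secondary-endpoint section do not fit together. The first names an outcome whose only post-baseline value falls in the third trimester. The second names the time points at which effects are estimated and leaves the third trimester out. An analyst who follows the second paragraph literally has no PES-Brief value to compare.

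HMHB is an anxiety-focused prenatal intervention. The Background ties anxiety during pregnancy to fetal growth, and Table 1 gives sessions 4 and 6 a component on fear of childbirth. PES-Brief is the measure closest to that target while the woman is still pregnant. If its comparison is not specified, a birth-outcome result in either direction cannot be set beside a pre-planned estimate of whether pregnancy anxiety changed. The time point, covariates and test would also be open to choice after the data are seen.

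**Working it through.** **Plan's own figures.** The point concerns timing, so no plan figure depends on it. As a check that the sample size is untouched, take 30% against 21% (a 30% relative reduction) and 85% power from Section III.B. Two-sided alpha of 0.05 is assumed, because the main-trial text does not state it. With no continuity correction:

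n = [1.960·√(2·0.255·0.745) + 1.036·√(0.30·0.70 + 0.21·0.79)]² / 0.09² = (1.208 + 0.635)² / 0.0081 ≈ 420 per arm

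420 / (1 − 0.30) = 600 per arm. Both match the plan and neither changes here.

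**Time points side by side.** The rule names two: birth and six weeks.

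| Measure | In the section's outcome list? | 3rd trimester | Birth | 6 weeks | Named time points with data |
|---|---|---|---|---|---|
| PES-Brief | yes | yes | no | no | 0 of 2 |
| PSS-10 (stress) | yes | yes | no | yes | 1 of 2 |
| MRQ (marital relationship) | yes | yes | no | yes | 1 of 2 |
| WHO-DAS (disability) | yes | yes | no | yes | 1 of 2 |
| MSPSS (social support) | no | yes | no | yes | 1 of 2 |
| PAAS (behavioural activation) | no | yes | no | yes | 1 of 2 |
| SGA in utero | no | yes | no | no | 0 of 2 |

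The earlier columns of the MRQ, WHO-DAS and MSPSS rows look shifted in the extracted table. Their third-trimester entries here are taken from the At 3rd trimester text. The six-week mark is clear in each row. PES-Brief is the only listed outcome in this set with no value at a named time point.

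**Is PES-Brief analysed anywhere else?**
- Mediation Analysis names stress, social support and empowerment.
- Moderator Analysis names social support, stress, marital relationship, empowerment and IPV.
- Analysis of Variables from Biological Substudy uses HADS for anxiety.

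None of them uses PES-Brief.

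**Who depends on it.** In Table 4, HADS is given to all women at screening and at six weeks; the administrations in between carry the substudy mark. The substudy takes 200 randomised women (100 per arm), and its 100 healthy controls are outside the randomisation. So 1,200 − 200 = 1,000 randomised women, before attrition, have PES-Brief as their only anxiety scale between randomisation and six weeks.

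**What the comparison could show.** Suppose 420 women per arm have a third-trimester score. That is an assumption: 420 is the plan's six-week figure. With two-sided alpha of 0.05, the detectable standardised difference is (1.960 + z_power)·√(2/420), which is 0.19 at 80% power and 0.22 at 90%.

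**What baseline adjustment adds.** Residual variance is multiplied by 1 − r², where r is the correlation between baseline and third-trimester scores. The documents give no r. At assumed values of 0.3, 0.5 and 0.6 the factor is 0.91, 0.75 and 0.64. This illustrates the gain from adjustment and does not measure the gap.

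**The case against.** The best defence is that the rule omits the third trimester without excluding it. The section sits under an efficacy heading, names PES-Brief as an outcome, says when it is measured, and states that in all regression models for primary and secondary endpoints the arm coefficient is the estimated effect. Read whole, it very likely intends a comparison at the one post-baseline visit. The form also asks only for a brief analysis plan, and Missing Data defers detail to a statistical analysis plan finalised before unblinding. Most of this stands: that PES-Brief would never be compared is an inference from one sentence. It does not close the gap. The supplied documents contain no fuller plan, and a later plan that carried the written rule forward would repeat the omission.

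A reader might also infer that the other third-trimester measures get no treatment comparison. The documents do not support that. Perceived stress, marital relationship and WHO-DAS are repeated at six weeks, where the rule covers them. Third-trimester stress and social support also enter the exploratory mediation models, which require modelling the mediator on arm. Social support and behavioural activation are not on the section's outcome list, and neither is in-utero SGA, so the absence of an efficacy test for them contradicts nothing.

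**Conclusion.** The point holds for PES-Brief alone. It is a listed outcome with data at none of the two time points named for effect estimation, and no other section gives it an analysis. The consequence is an unspecified comparison for one non-primary outcome. That outcome is the only anxiety scale between randomisation and six weeks for about 1,000 of 1,200 randomised women. Severity is minor: the primary endpoint, sample size and birth outcomes are unaffected.

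The conclusion rests on reading the effect-estimation sentence as the full list of time points, and on Table 4 being correct that PES-Brief is not collected at birth or six weeks. It does not show that the trial team means to leave the scale unanalysed.

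**What to change.** - Amend the rule in Analysis of Secondary Efficacy Endpoint(s) so that, besides birth and six-week measures, it names the third-trimester measure for PES-Brief.
- Specify the comparison: third-trimester PES-Brief between arms, adjusted for baseline PES-Brief, with the section's non-parametric test alongside. At present, regression on baseline characteristics is only a sensitivity analysis.
- Report by arm how many women lack the third-trimester visit because they delivered first. Preterm birth is itself a secondary outcome, so this missingness could differ between arms.

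The cost is one sentence, one model and one count. The data are already scheduled for collection and no sample-size figure changes. The amendment should be made before unblinding, in this section or in the statistical analysis plan to which it defers.

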### **Baseline**

Data will be collected on psychosocial factors (social support, quality of marital relationship, empowerment and functional disability, behavioral activation). We will also collect data on other socio-demographic variables including maternal age (years), maternal weight (kg), socio-economic assets (adapted from the Pakistan DHS), (44) marital status (married, single, widowed), education (years of formal education completed), and literacy (literate, semi-literate, not literate) and medically-related variables including gestational age of current pregnancy, number of pregnancies, history of SGA, LBW, PTB, stillbirth, and any complications in previous pregnancies/births. We will also collect data on current medications and current medical status, i.e. gestational diabetes, hypertension, anemia, mid-upper-arm circumference, smoking, substance abuse, and medication use for depression (though we expect these last three to be uncommon). An intimate partner violence (IPV) screening question will be administered so that referrals can be made if any women experience IPV. Women in the biological sub-study will also have their blood drawn (up to 20 mL) by a study clinician or a research assistant trained in phlebotomy. Each participant will be scheduled as close to possible to the same time of day during the morning hours for all four blood draws (as blood is drawn in HFH between 8:00am and 1:00 pm), allowing us to control for diurnal variation in cytokine levels. Blood will be collected in sodium-heparin tubes for immune cell preparation. Blood will be centrifuged within 8 hours of collection by low-density gradient centrifugation via a Z326 High Performance Centrifuge. Plasma will immediately be frozen in cryovials at -80 C in a ThermoScientific Revco RLE Ultra-Low Lab Freezer and will be stored there until it is shipped to Baltimore for analysis at the end of the trial.

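### Secondary scales with a pre-treatment score get a main test with no stated baseline adjustment, which costs precision but does not cause bias

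*Combined protocol and SAP*

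**What the plan says.** The section Analysis of Secondary Efficacy Endpoint(s) sets the order of analyses: "Primary analyses will be non-parametric tests, however sensitivity analyses will use parametric models such as linear and logistic regression to control for baseline values". It names no test. It plans to "compare the intervention and control groups in terms of changes in CMD symptom scores", by PHQ-9 and HADS anxiety, and for the secondary hypotheses "we will estimate the effects of the intervention using birth and follow-up (6 weeks postpartum) measures separately". The other listed outcomes include "maternal functioning (using WHO-DAS), marital relationships (MacArthur Relationship Questionnaire), IPV, women's empowerment" and PES-Brief. On estimation, "in all regression models the coefficient on the HMHB vs. non-HMHB (control group) indicator variable will be taken as the estimated effect".

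Pre-treatment scores exist for several of these. HADS anxiety is taken at screening from every woman, since a score of 8 or more is required for entry. The Baseline section lists "social support, quality of marital relationship, empowerment and functional disability, behavioral activation"; Table 4 places some of these scales in the Screening column, but either way they come before treatment. WHO-DAS, marital relationship, empowerment and HADS anxiety are repeated at six weeks, and PES-Brief in the third trimester. Table 4 shows PHQ-9 at six weeks only.

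Baseline Descriptive Statistics adds that the parametric models will adjust for variables found to be unequally distributed between the arms.

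**The concern.** When an outcome has been measured on the same scale before treatment, adjusting for that score is the usual way to sharpen the comparison. Here such adjustment is at most a sensitivity analysis, and even there it is not assured. The text speaks of the mothers' baseline characteristics in general, and the covariate rule works by observed imbalance, so a strongly prognostic baseline score that happens to be balanced could be left out.

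Two things are at stake. Secondary comparisons may miss effects that the collected data could show. In addition, the main p-value and the reported effect come from different analyses and can point different ways.

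HADS anxiety needs separate thought. If the wording on changes means a change score, the analysis fixes the slope on baseline at 1. The entry cut restricts the baseline range and probably weakens its correlation with a score taken months later, and a change score does worst when that correlation is low.

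**Working it through.** **The plan's own figure.** No power is stated for any secondary scale, so the evaluable sample size for the primary endpoint is the anchor. Inputs from the sample-size section: 30% prevalence, a 30% relative reduction (to 21%), 85% power, 30% attrition. Two-sided alpha of 0.05 is assumed; the documents state 0.05 only for the biological substudy.

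n = [1.960·√(2·0.255·0.745) + 1.036·√(0.30·0.70 + 0.21·0.79)]² / 0.09² = 419.6, so 420 per arm; 420/0.70 = 600 enrolled per arm. Both match the plan.

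**Reference effect.** At 80% power the non-centrality is 1.960 + 0.842 = 2.802. With 420 per arm this corresponds to d = 2.802·√(2/420) = 0.193 SD on the follow-up score.

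**Relative variances** (follow-up variance = 1, ρ = baseline to follow-up correlation, k = baseline SD / follow-up SD):
- follow-up score alone: 1
- change score: 1 + k² − 2ρk
- regression on own baseline: 1 − ρ²

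Power after adjustment = Φ(2.802·√(V_plan / (1 − ρ²)) − 1.960), where V_plan is the variance of the comparison it replaces. The documents give no ρ or k for these scales, so both are assumed.

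**If the comparison replaced is follow-up alone, at 80% power:**

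| ρ | 1 − ρ² | non-centrality | power after adjustment |
|---|---|---|---|
| 0.2 | 0.96 | 2.859 | 81.6% |
| 0.3 | 0.91 | 2.937 | 83.6% |
| 0.5 | 0.75 | 3.235 | 89.9% |
| 0.7 | 0.51 | 3.923 | 97.5% |

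**If the comparison replaced is a HADS change score, at 80% power:**

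| ρ | V_plan, k = 1 | power after adjustment | V_plan, k = 0.7 | power after adjustment |
|---|---|---|---|---|
| 0.2 | 1.60 | 95.1% | 1.21 | 88.2% |
| 0.3 | 1.40 | 93.5% | 1.07 | 85.9% |
| 0.5 | 1.00 | 89.9% | 0.79 | 82.0% |
| 0.7 | 0.60 | 86.0% | 0.51 | 80.0% |

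The k = 0.7 columns stand for a baseline SD narrowed by the entry cut. With k = 1 and ρ below 0.5 the change-score variance exceeds 1, so a change score is then noisier than ignoring baseline altogether.

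**Approximation.** These are normal-theory figures. An unadjusted rank test on normal data has efficiency of about 0.955, which moves the detectable difference from 0.193 to 0.193/√0.955 = 0.198 SD.

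**The case against.** The case for leaving the plan alone has real parts.

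- *The baseline is not ignored.* A reader might infer that the plan discards it. The documents do not support that: baseline-controlled regressions are planned, the estimated effect is a regression coefficient, and a change score also uses the baseline. What stands is the ordering and the unnamed covariate.
- *The wording is ambiguous.* That the rank tests are unadjusted is a fair inference, but it is not written. The HADS change score is also an inference: the same phrase covers PHQ-9, which has no pre-treatment score in Table 4, so it cannot literally mean a change score for both. The change-score figures are therefore conditional.
- *Not every scale measured twice is an outcome.* Social support (MSPSS) and behavioral activation (PAAS) are measured before treatment, but they are not in the secondary list. Social support appears as a mediator and moderator. The point does not extend to them.
- *The gain may be small.* Baseline is at 22 weeks' gestation or earlier and the main follow-up is six weeks postpartum, so low correlations are plausible. At ρ = 0.2 the gain over follow-up alone is under 2 points.
- *Ranks can beat least squares.* For skewed or heavy-tailed scores this is true, and robust standard errors do not restore efficiency. A rank-based or ordinal model that also adjusts for baseline meets the objection, provided it is chosen in advance.
- *Detail is deferred to a later SAP.* The Missing Data section says so, but the order of analyses is already fixed in the present text.

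**Conclusion.** The point holds for five listed outcomes: HADS anxiety, WHO-DAS, marital relationship, empowerment and PES-Brief. Their main analysis makes inefficient use of pre-treatment scores that are already collected, and it is separate from the regression that supplies the effect.

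Under the assumptions above, own-baseline adjustment adds about 2 to 18 points to an 80% power over ρ 0.2 to 0.7, compared with follow-up alone. Compared with a HADS change score, if that is what is meant, it adds about 15 to 6 points with equal SDs. With a baseline SD of 0.7 of the follow-up SD it adds about 8 points at ρ = 0.2, 6 at 0.3, 2 at 0.5 and none at 0.7.

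A reader might go on to infer biased treatment effects or a weakened trial. Neither follows. The arms are randomized, so the unadjusted comparisons remain valid, and the primary endpoint and its sample size are untouched. This is a worthwhile improvement to secondary analyses, of a size that the documents alone cannot settle.

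**What to change.** In Analysis of Secondary Efficacy Endpoint(s), for the five scales:

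1. Make the main analysis a regression of the follow-up score (six weeks; third trimester for PES-Brief) on arm and the same scale's screening or baseline score. Name that covariate for each scale, so that it does not depend on the imbalance rule.
2. Fix the form for each scale before unblinding: linear with robust standard errors, or a rank-based or proportional-odds version.
3. For HADS anxiety, use the six-week score as the outcome and screening HADS anxiety as the covariate, not the change.
4. State that PHQ-9 is compared at six weeks and not as a change.
5. Keep the unadjusted rank test as the sensitivity analysis. Test and estimate then come from one model.

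The cost is wording only: the data are already collected and regression is already planned. The small downside is some reliance on a model, which the retained rank test checks. The Missing Data section bases adjusted analyses on observed baseline covariates and leaves imputation to a sensitivity analysis. It should therefore also say how a woman with a missing baseline score stays in the main analysis.

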#### Analysis of Variables from Biological Substudy

**Statistical Analysis.** Oversight for the statistical analyses will be provided by [name] of the Johns Hopkins Biostatistics Center. The initial statistical approach will include a descriptive cross-sectional analysis at each time point, both for quality assurance and to attain a better understanding of the distributions of the outcome variables for use in subsequent analyses, including the need for any transformations, followed by the longitudinal analyses. For **Aim 1**, we will assess the associations between cytokine levels as dependent variables and level of anxiety (as measured by the HADS) as the independent variable. The level of anxiety will be considered from the following perspectives: 1) dichotomous (above and below HADS=8) and 2) continuous. In both analyses, we will compare women with anxiety vs. healthy controls and with and without the intervention to evaluate whether there is a positive association between

cytokines and other immune markers with anxiety. In addition, we will perform a comparison of immune markers between women disease/intervention groups adjusted for potential confounders that are differentially distributed by disease group, using multivariable linear regression model at each time point. We will assess whether association between immune marker and anxiety is different by group and by visit. In the longitudinal analyses, we will fit generalized linear mixed effect models to account for within-woman correlation of inflammatory markers. The model will include indicators for visit and group as well as any relevant interaction terms (e.g. group by visit). The models will adjust for baseline severity and other patient characteristics. A random effect for woman will be included as a random intercept. Other, more complex model structures will be explored, such as a model with random slope or non-independent residual correlation structure. These models account for missing at random, i.e. missing data are assumed to depend on prior immune marker values and covariates. Standard model checking will be performed and the most parsimonious model will be selected based on the Akaike Information Criterion (AIC).

For **Aim 2**, we will follow the same approach, with ALLO levels as the independent variables and anxiety as the dependent variable. Generalized linear mixed effects models will be fit to the data to model anxiety trajectories while accounting for within-women correlation of these measures. Estimated anxiety trajectories and ALLO levels will be used as candidate independent variables in a logistic regression model of risk of PPD. Cross-validated area under the curve will be used to assess model discrimination between women with and without PPD.

For **Aim 3**, we will assess the associations between ALLO levels and immune markers at different times during pregnancy by disease/intervention group and will fit similar generalized linear mixed effects models described in Aims 1 and 2. These models will first be fit for each immune marker separately and then combined into a multilevel model with crossed random effects that includes with random intercepts for woman and immune marker to “borrow information” across multiple immune markers within the woman.

For **Aim 4**, our analysis will focus on the association of perinatal anxiety and birth outcomes, specifically assessing mediation in both cross-sectional and longitudinal analyses partitioning the total effect of anxiety on birth outcomes as direct and indirect, through change in cytokine and hormone levels.

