This IRB application also covers a secondary study, to additionally study biological correlates of antenatal anxiety (i.e., immune and endocrine functioning) in a subset of women from the main trial: 200 drawn from our randomized trial (100 intervention, 100 usual care), as well as 100 healthy women without anxiety or depression. The aims of the secondary study are as follows:

**Aim 1:** To characterize the “immune phenotype” of anxious women across the peripartum, specifically by measuring the relation among anxiety symptoms and peripheral markers of inflammation (IL-6, CCL3, CXCL8, Eotaxin, VEGF, and GM-CSF, as supported by our preliminary data) within and across women (both anxious and healthy) and between those receiving the intervention and control.

**Aim 2:** To determine the relation between levels of allopregnanolone (ALLO) in pregnancy and 1) concurrent anxiety symptoms and 2) future symptoms of postpartum depression (PPD).

**Aim 3:** To examine the relation between changes in immune functioning (Aim 1) and ALLO levels (Aim 2) in anxious pregnancy across time.

**Aim 4:** To examine whether immune function and/or ALLO are mediators or moderators of the association between antenatal anxiety and poor birth outcomes (specifically, preterm birth and small-for-gestational age).

To supplement our study, we will collect qualitative data as part of a process evaluation to better understand women's experiences with the intervention (e.g. how it can be improved). Given the recent effects of COVID-19 on our participants and our study, we will also inquire about how the telephone format of our intervention is being received by our participants, as well as try to learn about the impact of social-distancing and other aspects of the COVID-19 situation on pregnant women generally.

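### Aims 1 and 3 of the biological substudy include a within-woman relation, but no term in the planned models isolates it; split HADS and ALLO into each woman's mean and her visit deviation

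*Combined protocol and SAP*

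**What the plan says.** In Section I, Aim 1 of the secondary study relates anxiety symptoms to inflammatory markers "within and across women (both anxious and healthy) and between those receiving the intervention and control". Aim 3 concerns "the relation between changes in immune functioning (Aim 1) and ALLO levels (Aim 2) in anxious pregnancy across time".

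The analysis is in Section V, item 4, under Analysis of Variables from Biological Substudy. The first aim's analysis is stated this way: "we will assess the associations between cytokine levels as dependent variables and level of anxiety (as measured by the HADS) as the independent variable", with HADS taken as "1) dichotomous (above and below HADS=8) and 2) continuous". Markers are also compared between groups, with confounder adjustment, "using multivariable linear regression model at each time point". On effect modification: "We will assess whether association between immune marker and anxiety is different by group and by visit". For the longitudinal fit the list of terms reads "The model will include indicators for visit and group as well as any relevant interaction terms (e.g. group by visit". Baseline severity and patient characteristics are added as adjustments, and "A random effect for woman will be included as a random intercept". Random slopes and other residual structures may be explored, with AIC choosing among models. Aim 3 uses similar mixed models for ALLO and the markers, by group.

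Two things are absent. No woman-mean and deviation terms, change score or fixed-effects model is described. And HADS does not appear in the list of longitudinal terms; its role there has to be inferred from the Aim 1 sentence.

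**The concern.** The across-women question is whether women who are generally more anxious have higher marker levels. The within-woman question is whether a woman's markers move when her anxiety moves. The two slopes can differ. The substudy joins women selected at HADS 8 or above with women below 8, and Section II itself notes that sleep, smoking, obesity and nutrition may be tied to both anxiety and inflammation. Stable differences of that kind feed the across-women slope only.

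A single time-varying predictor in a random-intercept model estimates a weighted average of the two slopes. A clear positive coefficient could then be read as markers tracking anxiety over time when no woman's markers changed with her anxiety. Section II hopes the substudy will suggest malleable biological targets, and for that purpose the within-woman slope is the more relevant evidence. It is also free of confounding by stable characteristics.

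**Working it through.** The plan gives no figure on this point. Its power statement (Section III.B) concerns differences in group means and does not cover a within-woman slope.

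**1. Aims against estimators**
- Intervention versus control: covered by the group and group-by-visit terms.
- Across women: covered by the per-visit regressions and the anxious-versus-healthy comparisons, though one visit's HADS carries that visit's fluctuation as well as the woman's usual level.
- Within women: no estimator. A random intercept models the correlation among a woman's outcomes. A random slope lets slopes vary among women. AIC chooses among such models. None of these changes what the average slope is made of.

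**2. Inputs**
- From Section III.B: four measurements and exchangeable correlation 0.6. With outcome variance scaled to 1, the intercept variance is 0.6 and the residual variance 0.4.
- Assumed, because the documents give no HADS variances: between-woman SD 3–5, within-woman SD 2–3.
- T, the number of visits with both HADS and blood: four if HADS is taken at every draw. It is three as listed, because the third-trimester section draws blood but does not name HADS.

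**3. Share of the between-woman slope, one predictor and no other terms**

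B = T × VarB / (0.4 + 0.6T); W = (T − 1) × VarW / 0.4; share = B / (B + W).

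| T | SD between / within | B | W | Share |
|---|---|---|---|---|
| 4 | 3 / 3 | 9 × 4/2.8 = 12.86 | 9 × 3/0.4 = 67.5 | 16% |
| 4 | 5 / 2 | 25 × 4/2.8 = 35.71 | 4 × 3/0.4 = 30 | 54% |
| 3 | 3 / 3 | 9 × 3/2.2 = 12.27 | 9 × 2/0.4 = 45 | 21% |
| 3 | 5 / 2 | 25 × 3/2.2 = 34.09 | 4 × 2/0.4 = 20 | 63% |

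This ignores the noise in a woman's observed mean. Allowing for it adds VarW / (0.4 + 0.6T) to the denominator. The lowest figure becomes 12.86 / (80.36 + 3.21) = 15% and the highest 34.09 / (54.09 + 1.82) = 61%, so little changes.

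**4. Effect of the terms the plan does list**

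A simulation used 60 data sets per scenario, three groups of 60 women, four complete visits and the variances in step 2. HADS was in SD units, with assumed intraclass correlation 0.5 within groups and the two anxious groups shifted up by 1.5. Mean estimates:

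| Model | True within 0, between 0.3 | True within 0.3, between 0 |
|---|---|---|
| Regression at one visit | 0.22 | 0.08 |
| Mixed model, visit + single HADS term | 0.08 | 0.22 |
| + group | 0.05 | 0.26 |
| + group + baseline HADS | 0.02 | 0.29 |
| Split: deviation slope | 0.00 | 0.31 |
| Split: mean slope | 0.28 | 0.02 |

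The formula in step 3 agrees with this. The group shift adds 1.5² × (2/3) × (1/3) = 0.5 to a between-woman variance of 0.5, so VarB = 1.0 and VarW = 0.5. The share is 1.429 / (1.429 + 3.75) = 0.276, and 0.276 × 0.3 = 0.083, against 0.081 simulated. With group in the model VarB = 0.5: 0.714 / (0.714 + 3.75) = 0.160, and 0.160 × 0.3 = 0.048, against 0.051 simulated. When both true slopes are 0.2, every model returns about 0.20.

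**5. ALLO in Aim 3**

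The groups are defined by anxiety and allocation, and the plan does not tie baseline severity to ALLO. These terms need not absorb stable differences in ALLO between women, so the shrinkage in step 4 cannot be assumed for Aim 3. The documents give no ALLO variances, so no share is computed.

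**The case against.** A reader might infer that neither part of Aim 1 is answered. The documents do not support that. The per-visit regressions and the anxious-versus-healthy comparisons address the across-women part without any blended coefficient, and the intervention contrast has its own terms. Only the within-woman part lacks an estimator.

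A reader might also infer that the planned model would report 16–63% of the between-woman slope. That range belongs to a model with HADS alone. The plan adds group indicators, which take out the separation between the anxious and healthy groups, and adjusts for baseline severity and patient characteristics. If baseline severity means baseline HADS, little mixing remains: 0.02 of a between-woman slope of 0.3 in the simulation. This objection stands for HADS as far as it goes. But baseline severity is undefined, so how close the coefficient comes to a within-woman slope rests on an unstated choice, and the argument does not carry over to ALLO.

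Three further points are fair. The single time-varying term is inferred, and the plan lets the association vary by group and visit; that still gives no within-woman term. Aim 2 does not ask for a within/across distinction, so the point is not pressed there. Finally, the section is a brief plan, and the Missing Data paragraph defers detail to a statistical analysis plan to be finalized before unblinding. That gives a place to add the split, but it does not supply one.

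**Conclusion.** The point holds for the within-woman part of Aim 1 and for the change-over-time question in Aim 3: the stated methods contain no term that isolates it, and none of the listed model options would create one. If HADS enters as a single time-varying predictor with no other terms, the between-woman share is 16–54% with four HADS visits and 21–63% with three, given outcome correlation 0.6 and the assumed HADS SDs. These figures describe the unadjusted model and are not the bias to expect. Group indicators lower the share, and baseline HADS would lower it much further. Mixing does harm only if the two slopes differ, which the documents make plausible but do not show. This is an inexpensive improvement to a secondary study and does not touch the trial's primary analysis.

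**What to change.** In the longitudinal models for Aim 1 (HADS) and Aim 3 (ALLO):

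- Keep the visit indicators.
- Subtract the visit mean from the predictor first. ALLO rises steeply through pregnancy and the plan allows for up to 40% attrition, so a raw mean would depend on which visits a woman attended.
- Enter each woman's mean of the centred values and her visit-specific deviation from it as two terms.
- Report the deviation slope as the within-woman answer and the mean slope as the across-women answer. If group indicators stay in, say that the mean slope compares women within the same group.
- Define baseline severity. If it is baseline HADS, it overlaps with the woman's mean, and the plan should say how both are handled.

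The cost is one or two derived variables per predictor and no new data. The within-woman interval is wider than the blended one by a factor 1/√w, where w = W / (W + B) is the weight on the within slope. Here B also counts the noise in the observed mean, and the HADS intraclass correlation (ICC) is assumed. With ICC 0.5 and four visits, W = 3 × 0.5/0.4 = 3.75, B = 2.5/2.8 = 0.893 and w = 0.808, so the interval is 1.11 times as wide. With three visits w = 0.733 and the factor is 1.17. Over ICC 0.2–0.8 the factor runs from 1/√0.913 = 1.05 (four visits) to 1/√0.458 = 1.48 (three visits).
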